## **Background**

The frequency of surgical procedures that can be performed laparoscopically is rapidly increasing. Surgical conditions in laparoscopic surgery are largely determined by the depth of neuromuscular relaxation during surgery. Neuromuscular blockade (NMB) is frequently utilized in laparoscopic procedures to improve surgical conditions by relaxing the abdominal muscles and thus facilitating insufflation with CO2 to optimize surgical view. While studies have investigated the effects of neuromuscular blockade on surgical conditions and abdominal insufflation pressures, to our knowledge, little is known about the benefit, if any, a deep NMB blockade will have over a moderate NMB on airway pressures. Increased airway pressures can lead to an increase in alveolar and perivascular edema, a decline in dynamic lung compliance and hypoxemia. A deep neuromuscular blockade could decrease the resistance to ventilation by increasing the compliance of the chest and abdominal wall, thereby allowing maximization of lung expansion at lower airway pressures.

Several studies have investigated surgical view under deep vs. moderate neuromuscular blockade. Across a single intraabdominal insufflation pressure, a deep neuromuscular blockade may provide better surgical conditions than a moderate block. Raising the intraabdominal insufflation pressure can result in several adverse outcomes such as increased airway pressures, postoperative pain, risk of CO2 embolism, and hemodynamic disturbances. Low insufflation pressures of < 12 mm Hg have been associated with fewer adverse effects than higher pressures (>15 mm Hg). Though studies have shown that surgical view under deep block is statistically superior to the view under a moderate NMB block across a single insufflation pressure, the primary outcome in these studies was a subjective, 5 point scale requiring the surgeon to grade his surgical view. Hence, there is a lack of objective outcomes assessed in these studies. Measuring the peak airway pressures in the deep vs. moderate block group will provide us with an objective indice to use in making the determination if one type of block is ‘superior’ to the other.

Additionally, the degree of neuromuscular block for optimal surgical procedures has been the focus of debate and research for several years. Firstly, different muscle groups have different sensitivity to neuromuscular blocking agents (NMBA). For example, though neuromuscular blockade is often measured at the adductor pollicis muscle in the thumb, the abdominal muscles and diaphragm are less sensitive to NMBA. Consequently, surgeons may complain of insufficient NMB though the anesthesiologist observes no twitches at the thumb. Thus, some authors have argued that paralysis of the diaphragm and the abdominal wall muscles can only be

ensured by an intense NMB, quantified by post-tetanic count (PTC) of 1. However, these results must be counterbalanced by the need for optimal extubating conditions which cannot occur unless there is full reversal of muscle paralysis, a condition which requires the presence of at least 1-2 twitches (if one uses the traditional drug, neostigmine, to antagonize paralysis which would not needed if we use the newly FDA approved drug, sugammadex). Thus, a deep block throughout the procedure carries the inherent risk of delaying extubation if sugammadex is not available.

The Table below shows known and theoretical risks/benefits related to deep vs medium NMB.

Deep NMB	Medium NMB
Literature supports better operating conditions/view by surgeon	Literature supports worse operating conditions/view by surgeon
Possibly lower airway pressures	Possibly worse airway pressures
Possibly longer duration to extubation	Possibly shorter duration to extubation
Possibly worse respiratory mechanics at the end of anesthesia	Possibly better respiratory mechanics at the end of anesthesia

Thus, there is clearly equipoise with regard to the comparative effectiveness of deep vs medium NMB. Therefore, we wish to ascertain if a deep neuromuscular block will decrease the airway pressures in patients undergoing laparoscopic procedures compared to those under a moderate block. A reduction in airway pressures may lead to a decrease in the complications associated with elevated airway pressures including hypoxemia, total static lung compliance, alveolar edema, and long term morbidity. Additionally, we wish to understand if time from administration of sugammadex to reversal is different between patients that have a moderate NMB as compared to a deep NMB.

To test our hypotheses, we will conduct a two period cross-over study by randomizing patients undergoing laparoscopic surgery into 2 different groups: group 1 in which patients will receive “deep neuromuscular blockade” in the beginning portion of the surgery followed by a period of “moderate blockade”, and group 2 in which patients will receive “moderate neuromuscular blockade” in the beginning portion of the surgery followed by a period of “deep blockade”. The deep neuromuscular block will be defined as post tetanic count of 0 to 2 and the moderate neuromuscular block will be defined as 1-2 twitches. In all patients, sugammadex will be used to reverse the block at the end of surgery in order to obtain optimal extubating conditions. Time from administration of sugammadex to extubation will be calculated and compared.

### **Hypothesis**

A deep neuromuscular blockade results in lower peak airway pressures and lower abdominal insufflation pressures in patients undergoing elective laparoscopic procedures.

## **Objectives**

Primary Outcome: Peak Airway Pressures

Secondary outcomes:

- Hemodynamics (blood pressure (BP), Heart rate (HR)) measured q15 min at the time of airway pressure measurement
- Duration from administration of sugammadex (to be given at skin closure) to Train of Four (TOF) ratio = 0.7, 0.8 and 0.9 and extubation using the following guidelines (SpO2 >98% on 100% FiO2, Respiratory rate (RR) <35, tidal volume (TV) > 5 ml/kg, RR/Tidal Volume <100)
- Recovery variables in the post-anesthesia care unit (respiratory rate, arterial oxygen saturation, numerical pain rating, nausea or vomiting, and level of sedation or alertness).
- Adverse events (AE).

## **Methods**

This will be a single-center, prospective, randomized, two-period crossover controlled trial. Approval from the local IRB will sought and patients will provide written informed consent.

### **Inclusion and exclusion criteria**

Inclusion criteria:

The participant must fulfill ALL the criteria listed below for entry.

- Each participant must be willing and able to provide written informed consent for the study.
- Each participant must be greater than or equal to 18 years of age.
- Each participant must be ASA class I, II or III.
- Each participant must be scheduled for elective laparoscopic surgery (this includes robotic laparoscopic s).
- Expected surgical duration of 60 min or longer

Exclusion criteria:

- Inability to give informed oral or written consent
- Known or suspected neuromuscular disorders impairing neuromuscular function;
- True allergies as defined as hypotension, bronchospasm, or anaphylaxis to muscle relaxants, anesthetics or opioids
- A history (patient or family) of malignant hyperthermia
- A contraindication for neostigmine administration
- Renal insufficiency, as defined by serum creatinine levels at 2.5 fold the normal level
- Body mass index >45 kg/m
- Significant respiratory disease.
- Planned postoperative mechanical ventilation

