## Investigational plan and treatments (see Figure 1)

Subjects will be randomly assigned to one of two study groups using a random number generator and sealed envelope technique:

Group 1 D→M: After induction and intubation, the patient will be maintained in a “deep” (post-tetanic count of zero to two) neuromuscular block (NMB). Deep NMB will be obtained with an intubating dose of rocuronium of 0.5 mg/kg or as per clinical team’s discretion. After surgical incision is made, the abdomen is insufflated, trocars are inserted, and prior to the beginning of the actual laparoscopic procedure, collection of data for “deep” NMB period will begin. Neuromuscular blockade level will be maintained and adjusted throughout the course of surgery using intravenous bolus doses of rocuronium. Dosing of rocuronium will be determined by the clinical team. Only the clinical team will administer any medications or fluids to patients enrolled in the study (no research team members will be administering drug or fluid). The surgeon will inform the study team member of the first Surgical Rating Scale (SRS) score for his/her view, and simultaneously, the first peak airway pressure and related variables will be collected (T0). For the next 20 minutes of surgery during which a “deep” NMB is being maintained, peak airway pressure, heart rate, and blood pressure will be collected every minute by the study team member (as per the anesthesia machine’s readings), and the surgeon will provide the SRS score every 5 minutes. To minimize any type of carry-over effects, after the completion of the deep NMB 20 minute period, a “transition period” will begin (T1).

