Upon successful acclimation to a “moderate” NMB, data collection may begin again (T2): the surgeon will again provide the SRS score simultaneously with the commencement of collection for peak airway pressure and related values. For the next 20 minutes of surgery during which a “moderate” NMB is maintained, peak airway pressure measurements (as well as other relevant secondary outcome measurements) will be collected every minute by the study team member by looking at the anesthesia machine’s readings and the surgeon will provide the SRS score every 5 minutes. After 20 minutes (T3), the patient will remain at the “moderate” NMB for the duration of the surgery unless a change in the depth of blockade is requested by the surgeon. Should such a request be made, this will be documented in the data collection (obtained from anesthesia record) along with the depth of blockade that the patient was switched to. By skin closure, the patient’s NMB will be returned to “moderate.”

Group 2 M→D: After induction and intubation, the patient will be maintained in a “moderate” (one or two twitches) neuromuscular block (NMB). Moderate NMB will be obtained with intubating dose of rocuronium of 0.5 mg/kg or as per clinical team’s discretion. After surgical incision is made, the abdomen is insufflated, trocars are inserted and prior to the beginning of the actual laparoscopic procedure, collection of data for “moderate” NMB period will begin. Neuromuscular blockade level will be maintained and adjusted throughout the course of surgery

using intravenous bolus doses of rocuronium. Dosing of rocuronium will be determined by the clinical team. Only the clinical team will administer any medications or fluids to patients enrolled in the study (no research team members will be administering drug or fluid). The surgeon will inform the study team member of the first SRS score for his/her view, and simultaneously, the initial peak airway pressure and related values are collected (T0). For the next 20 minutes of surgery (during which a “moderate” NMB is being maintained), peak airway pressure measurements, heart rate, and blood pressure will be collected every minute by the study team member by looking at the anesthesia machine’s readings, and the surgeon will provide the SRS score every 5 minutes.

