To minimize any type of carry-over effects, after completion of the moderate NMB 20 minute period, a “transition period” will begin (T1). During this “transition period” additional IV bolus doses of rocuronium will be administered to the patient to achieve “deep” neuromuscular blockade. Upon successful acclimation to a “deep” NMB, data collection may begin again (T2): the surgeon will again provide the SRS score simultaneously with the commencement of collection for peak airway pressure and related values. For the next 20 minutes of surgery (during which a “deep” NMB is maintained), peak airway pressure measurements (as well as other relevant secondary outcome measurements) will be collected every minute by the study team member by looking at the anesthesia machine’s readings, and the surgeon will provide the SRS score every 5 minutes. After 20 minutes (T3), the patient’s “deep” NMB will be maintained for the duration of the surgery unless a change in the depth of blockade is requested by the surgeon. Should such a request be made, this will be documented in the data collection (obtained from the anesthesia record) along with the depth of blockade that the patient was switched to. By skin closure, the patient’s depth will be returned to “deep.”

(Both Group 1 and Group 2): At skin closure, subjects in both groups will be reversed with sugammadex 4 mg/kg or at the discretion of the clinical team (T4). Patients will be extubated when the TOF ratio becomes 0.9 or higher (T5). Time from administration of sugammadex to extubation will be recorded.

In the recovery room (T6), the following variables will be measured by the study coordinator at 15 min intervals for the first 1 hour: respiratory rate, arterial oxygen saturation, numerical pain rating (on a scale from 0, no pain, to 10, most severe pain imaginable), occurrence of nausea or vomiting, and level of sedation or alertness. Additionally, the patient’s maximum inspired volume will be assessed 30 minutes after arrival in the PACU via the use of an incentive spirometer. After one hour, all measurements will be complete (T7).

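### The 60-minute surgical-duration criterion is not sized to the crossover schedule, so some patients may not supply a full second window, plausibly more often in the deep-to-moderate sequence

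*Combined protocol and SAP*

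**What the plan says.** The eligibility list (Inclusion and exclusion criteria) asks for "Expected surgical duration of 60 min or longer". It does not say from which event to which event duration is counted.

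The schedule is in Investigational plan and treatments:

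- **Start of period 1 (T0).** Readings start late in the access phase: "After surgical incision is made, the abdomen is insufflated, trocars are inserted, and prior to the beginning of the actual laparoscopic procedure, collection of data" begins. The same holds for Group 2.
- **Window lengths.** Each window lasts 20 minutes. In Group 1 the transition begins "after the completion of the deep NMB 20 minute period", and the second window closes with "After 20 minutes (T 3 ), the patient will remain at the" moderate level.
- **Deep to moderate (Group 1).** The only condition on restarting is "Upon successful acclimation to a “moderate” NMB, data collection may begin again". No duration, cap or active means is described.
- **Moderate to deep (Group 2).** "During this “transition period” additional IV bolus doses of rocuronium will be administered to the patient to achieve “deep” neuromuscular blockade". No duration is given here either.
- **Reversal.** In both groups sugammadex is described only at skin closure.

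The Statistical Analysis section compares peak airway pressure between conditions with a paired t-test or signed-rank test on per-patient summaries. It allows up to 20 minutes of readings per period and sets no minimum. A mixed model with treatment and time as fixed effects is added. The Power analysis needs about 52 patients and plans to enrol about 120.

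**The concern.** The floor is on the whole operation, while the measurements occupy only the part between trocar insertion and the end of the laparoscopic phase. Read literally, the criterion lets a site randomise patients whose operation may end before the second window is complete.

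Two things follow. A patient with no second-period readings drops out of the paired primary test, and one with a few readings enters with the same weight as a patient with twenty. Also, the two transitions are not alike as described: one is driven by drug, while the other appears to wait for recovery from a post-tetanic count of 0–2 to one or two twitches. If the second is slower, losses and truncation fall mainly on one sequence.

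Unequal completion by itself does not bias a within-patient difference. It does so when combined with a period effect, because the paired test relies on equal sequence sizes to cancel that effect. A period effect is credible here: the first window opens before the laparoscopic work proper starts, and the second falls later in the operation.

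**Working it through.** **1. The plan's own figure.** Inputs from the Power analysis: difference 1.48 mmHg, SD 3.68 mmHg (taken as the SD of the within-patient difference), two-sided α 0.05. The noncentral t distribution gives 81.2% power at n = 52, so the stated 81% is reproduced. Going from 120 to 52 tolerates a loss of 68/120 = 56.7%.

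**2. Time budget at the threshold.** Documented inputs: 60 min and two windows of 20 min. 60 − 2 × 20 = 20 min for access, transition and closure together. The documents give none of these three times. Under assumed values, the time left for the transition is:

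| Access (min) | Closure (min) | Left for transition (min) |
|---|---|---|
| 5 | 5 | 10 |
| 10 | 10 | 0 |
| 15 | 10 | −5 |

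A 60-minute case fits two full windows only if everything else takes 20 min or less.

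**3. How unequal completion enters the result.** Let τ be the deep-minus-moderate effect and π the period 2 minus period 1 effect. The expected difference is τ − π in a D→M patient and τ + π in an M→D patient. Over nDM and nMD completers, the paired mean estimates

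τ + π × (nMD − nDM)/(nMD + nDM).

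**4. Illustrative size.** All of these inputs are assumptions: 60 randomised per sequence; actual durations lognormal with median 100 min and log-SD 0.4, none below 60 min; access 10–15 min; closure 10 min; transition 5 min for M→D and 30 min for D→M.

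- D→M needs (10 to 15) + 20 + 30 + 20 + 10 = 90 to 95 min.
- M→D needs (10 to 15) + 20 + 5 + 20 + 10 = 65 to 70 min.
- The completing fraction is P(T > need)/P(T > 60), which gives 40 v 57 completers (access 10) or 37 v 54 (access 15).
- The multiplier is (57 − 40)/97 = 0.175 or (54 − 37)/91 = 0.187.
- If M→D patients need 5 min longer before T0 than D→M patients, the comparison is 40 v 54, and 14/94 = 0.149.

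The multiplier is therefore about 0.15 to 0.19. If the period effect were as large as the planned treatment effect, the shift would be 0.15 × 1.48 = 0.22 to 0.19 × 1.48 = 0.28 mmHg. The documents give no period effect, so this is only a scale.

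**5. Sensitivity.**

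| Scenario | D→M v M→D | Multiplier |
|---|---|---|
| D→M transition 20 min | 44–47 v 54–57 | about 0.10 |
| D→M transition 45 min | 27–30 v 54–57 | 0.31–0.33 |
| 30 min, median duration 120 | 45–48 v 57–59 | 0.10–0.12 |
| 30 min, any second-period reading counts | 51–54 v 60 | 9/111 = 0.08 to 6/114 = 0.05 |

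**6. Power under the worst row.** 27 + 54 = 81 completers still give about 95% power.

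**The case against.** A reader might infer that patients near the threshold cannot complete the schedule. The documents do not support that. The criterion is a floor on expected duration and says nothing about the actual case mix, and a 60-minute case with 20 min or less of other steps fits.

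A reader might also take greater loss from D→M as established. It is not. No transition times or completion rates appear, and Figure 1, which may carry a timeline, is not shown in the text available. Group 2 has a sentence on how its transition is achieved and Group 1 has no visible counterpart, which could be lost text. Group 2 is also given the same nominal intubating dose and may itself wait for a moderate block before T0, which narrows the gap.

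A shortened second window is not a lost patient, because the analysis accepts fewer than 20 readings. The mixed model can use patients with only period 1 data, and its time term might absorb a period effect, depending on how time is coded, which is not stated. Each patient is also their own control, so differing completer groups do not bias the paired difference unless there is a period effect or a treatment effect that varies with duration. Power is well protected.

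All of this stands, and it reduces the size and certainty of the point. It does not remove the 20-minute remainder, the open-ended transition, the lack of a minimum window, or the missing period term in the paired test.

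**Conclusion.** The point holds in a limited form. The 60-minute criterion is not matched to a schedule that needs 40 min of readings plus an uncapped transition after trocar insertion, and applying it literally will randomise some patients who may give a truncated second window or none. That much follows from the documents alone.

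That the loss is greater in D→M is a reasonable inference from the two transitions as described, not a finding. On that inference, the paired estimate shifts by about 0.15 to 0.19 of the period effect for full-window completers (30-minute D→M transition, median duration 100 min). It shifts by 0.05 to 0.08 if any second-period data count, and by nothing if there is no period effect. The figures depend on assumed access, transition and closure times and an assumed duration distribution. The remedy is cheap enough to be worth making before enrolment.

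**What to change.** Replace the criterion with a minimum expected time from trocar insertion to desufflation, equal to 40 min plus the longest transition the centre expects in the slower sequence. For example, 40 + 35 = 75 min if that transition is 35 min, and 40 + 45 = 85 min if it is 45. The figure must come from the centre's own timings; neither example is a recommended value. Any wait in Group 2 before T0 should be counted when deciding which sequence is slower. Apply the rule identically to both groups before the envelope is opened, so that eligibility cannot depend on the allocation.

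Three short additions to the analysis text would go with it: a minimum usable window, the handling of patients without period 2 data, and a report of completion by sequence. A period term in the primary comparison would remove the dependence on equal sequence sizes.

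The cost is a one-line eligibility amendment, somewhat slower screening, and results that apply to longer procedures. The cases excluded are mostly those that would have given truncated or no second-period data. The criterion would still rest on expected duration, so some operations will end early anyway.

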## Investigational plan and treatments (see Figure 1)

Subjects will be randomly assigned to one of two study groups using a random number generator and sealed envelope technique:

Group 1 D→M: After induction and intubation, the patient will be maintained in a “deep” (post-tetanic count of zero to two) neuromuscular block (NMB). Deep NMB will be obtained with an intubating dose of rocuronium of 0.5 mg/kg or as per clinical team’s discretion. After surgical incision is made, the abdomen is insufflated, trocars are inserted, and prior to the beginning of the actual laparoscopic procedure, collection of data for “deep” NMB period will begin. Neuromuscular blockade level will be maintained and adjusted throughout the course of surgery using intravenous bolus doses of rocuronium. Dosing of rocuronium will be determined by the clinical team. Only the clinical team will administer any medications or fluids to patients enrolled in the study (no research team members will be administering drug or fluid). The surgeon will inform the study team member of the first Surgical Rating Scale (SRS) score for his/her view, and simultaneously, the first peak airway pressure and related variables will be collected (T0). For the next 20 minutes of surgery during which a “deep” NMB is being maintained, peak airway pressure, heart rate, and blood pressure will be collected every minute by the study team member (as per the anesthesia machine’s readings), and the surgeon will provide the SRS score every 5 minutes. To minimize any type of carry-over effects, after the completion of the deep NMB 20 minute period, a “transition period” will begin (T1).

Upon successful acclimation to a “moderate” NMB, data collection may begin again (T2): the surgeon will again provide the SRS score simultaneously with the commencement of collection for peak airway pressure and related values. For the next 20 minutes of surgery during which a “moderate” NMB is maintained, peak airway pressure measurements (as well as other relevant secondary outcome measurements) will be collected every minute by the study team member by looking at the anesthesia machine’s readings and the surgeon will provide the SRS score every 5 minutes. After 20 minutes (T3), the patient will remain at the “moderate” NMB for the duration of the surgery unless a change in the depth of blockade is requested by the surgeon. Should such a request be made, this will be documented in the data collection (obtained from anesthesia record) along with the depth of blockade that the patient was switched to. By skin closure, the patient’s NMB will be returned to “moderate.”

Group 2 M→D: After induction and intubation, the patient will be maintained in a “moderate” (one or two twitches) neuromuscular block (NMB). Moderate NMB will be obtained with intubating dose of rocuronium of 0.5 mg/kg or as per clinical team’s discretion. After surgical incision is made, the abdomen is insufflated, trocars are inserted and prior to the beginning of the actual laparoscopic procedure, collection of data for “moderate” NMB period will begin. Neuromuscular blockade level will be maintained and adjusted throughout the course of surgery

using intravenous bolus doses of rocuronium. Dosing of rocuronium will be determined by the clinical team. Only the clinical team will administer any medications or fluids to patients enrolled in the study (no research team members will be administering drug or fluid). The surgeon will inform the study team member of the first SRS score for his/her view, and simultaneously, the initial peak airway pressure and related values are collected (T0). For the next 20 minutes of surgery (during which a “moderate” NMB is being maintained), peak airway pressure measurements, heart rate, and blood pressure will be collected every minute by the study team member by looking at the anesthesia machine’s readings, and the surgeon will provide the SRS score every 5 minutes.

To minimize any type of carry-over effects, after completion of the moderate NMB 20 minute period, a “transition period” will begin (T1). During this “transition period” additional IV bolus doses of rocuronium will be administered to the patient to achieve “deep” neuromuscular blockade. Upon successful acclimation to a “deep” NMB, data collection may begin again (T2): the surgeon will again provide the SRS score simultaneously with the commencement of collection for peak airway pressure and related values. For the next 20 minutes of surgery (during which a “deep” NMB is maintained), peak airway pressure measurements (as well as other relevant secondary outcome measurements) will be collected every minute by the study team member by looking at the anesthesia machine’s readings, and the surgeon will provide the SRS score every 5 minutes. After 20 minutes (T3), the patient’s “deep” NMB will be maintained for the duration of the surgery unless a change in the depth of blockade is requested by the surgeon. Should such a request be made, this will be documented in the data collection (obtained from the anesthesia record) along with the depth of blockade that the patient was switched to. By skin closure, the patient’s depth will be returned to “deep.”

(Both Group 1 and Group 2): At skin closure, subjects in both groups will be reversed with sugammadex 4 mg/kg or at the discretion of the clinical team (T4). Patients will be extubated when the TOF ratio becomes 0.9 or higher (T5). Time from administration of sugammadex to extubation will be recorded.

In the recovery room (T6), the following variables will be measured by the study coordinator at 15 min intervals for the first 1 hour: respiratory rate, arterial oxygen saturation, numerical pain rating (on a scale from 0, no pain, to 10, most severe pain imaginable), occurrence of nausea or vomiting, and level of sedation or alertness. Additionally, the patient’s maximum inspired volume will be assessed 30 minutes after arrival in the PACU via the use of an incentive spirometer. After one hour, all measurements will be complete (T7).

Intraoperative and postoperative data will be collected by a research coordinator who is not blinded to the patient’s randomization. The research coordinator will not be directly involved with the patient’s care. Rather, his/her sole purpose will be to record the relevant data (airway pressures, abdominal insufflation pressures, PACU indices etc.) every 1 minute. The coordinator will have

access to the electronically recorded patient data and will make their recordings directly from the anesthesia machine and/or the electronic anesthesia record. The research coordinator will also review data from the patient's chart (anesthesia record, PACU record) after surgery to collect any additional information that may be necessary.

